2 PARTICIPANTS

2.1 Participants. Describe the general characteristics of the subject populations or groups, including age range, gender, health status, and any other relevant characteristics.

Aim 1 & 2: Fifteen children, 9-11 years with JIA, and their parent will be recruited from the Rheumatology clinic at Seattle Children's Hospital (SCH). In Washington State, over 6,100 children have been diagnosed with JIA. Approximately 500 patients with JIA are seen each year in the Department of Rheumatology, and 250 are between 9 to 11 years.

Aim 3: Sixty children, 8-13 years, diagnosed with JIA and one parent will be recruited from the Pediatric Rheumatology Clinic at SCH and at The Children's Hospital of Philadelphia (CHOP), and remotely via flyers on social media.

Girls and boys are eligible, although we expect to enroll more Caucasian girls because of the heightened disease prevalence among Caucasian girls, and its relatively low prevalence in underrepresented minorities and boys.

2.2 Inclusion and exclusion criteria. Describe the specific criteria you will use to decide who will be included in your study from among interested or potential subjects. Define any technical terms in lay language.

Inclusion criterion for JIA children: 1) diagnosed with JIA; 2) 8-13 years; 3) able to read/speak English; and 4) parent report that child has difficulties with sleep quality (difficulty falling asleep, no bedtime routine, waking up in the middle of the night and struggling to fall back asleep) and/or poor sleep impacts their child's day to day function (school, interacting with peers, hobbies).

Exclusion criteria for JIA children include: (a) diagnosed sleep disorder (obstructive sleep apnea [OSA]); 2) positive screen on the Pediatric Sleep Questionnaire (> 0.33) for OSA (we will suggest follow up with the child's primary care provider because treatment of this condition is beyond the scope this intervention); 3) lack of daily access to the Internet or mobile device as the study will be conducted online; 4) developmental delay; d 5) children who do not speak English; and 6) child is not currently participating in psychological therapy.

Inclusion criteria for parents: 1) > 18 years; 2) able to read/speak English; 3) access to a computer or web-based device to complete surveys.

Exclusion criteria for parents: 1) diagnosed with a chronic illness that would interfere with ability to complete study procedures; 2) lack of daily access to the Internet or mobile device.

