Aims 1 & 2: Interested potential participants will contact the CRA by phone. For those who contact the CRA by phone, the CRA will screen potential participants initially over the phone (see Aims 1_2 Recruitment Script).

Aims 3: Interested potential participants may choose to visit <https://www.sleepsmartstudy.org/webpage> or contact the CRA by phone. For those who contact the CRA by phone, the CRA will screen potential participants initially over the phone (see Recruitment Script). For those who are eligible and interested, they will be directed to the <https://www.sleepsmartstudy.org/webpage> webpage (hosted by REDCap). From there, parents may complete the screening surveys including “does your child has difficulty with sleep quality and/or does poor sleep impact your child’s day-to-day function (school, interacting with peers, hobbies)?” Sleep-Related Breathing Disorder Scale from the Pediatric Sleep Questionnaire (SRBD) and is your child currently receiving psychological therapy. Instruments are automatically scored within REDCap and indicates whether participants appear to meet eligibility criteria or not. Those who are not eligible are thanked for their time. Those that are eligible are advised that the study team will contact them (see recruitment follow-up script).

REDCap uses unique identifiers for potential participants and only the CRA and PI has the master list connecting potential participant email, names, and identifiers.

4.2 Recruitment materials.

a. What materials (if any) will you use to recruit and screen subjects?

Examples: talking points for phone or in-person conversations; video or audio presentations; websites; social media messages; written materials such as letters, flyers for posting, brochures, or printed advertisements; questionnaires filled out by potential subjects.

Aim 1 & 2: Study flyer, letters to participants, Child Sleep Habits Questionnaire (CSHQ), Sleep-Related Breathing Disorder Scale from the Pediatric Sleep Questionnaire (SRBD) will be used to recruit and screen subjects.

Aim 3: Study flyer, letters to participants, social media posts, <https://www.sleepsmartstudy.org/webpage> , phone scripts, “does your child has difficulty with sleep quality and/or does poor sleep impact your child’s day to day function?” Sleep-Related Breathing Disorder Scale from the Pediatric Sleep Questionnaire (SRBD), and parent report if the child is currently receiving psychological therapy will be used to recruit and screen subjects.

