Examples: names and contact information; the information gathered from records that were screened; results of screening questionnaires or screening blood tests; Protected Health Information (PHI) from screening medical records to identify possible subjects.

Screening information includes:

Parent first name, email address, phone number, and preferred mode of contact (text, phone, email) for follow-up.

Also includes child first name, age, gender, and duration of JIA will be obtained to ensure study eligibility, and be retained as part of the study data. Additional information includes screening surveys: “does your child has difficulty with sleep quality and/or does poor sleep impact your child’s day to day function?” and Sleep-Related Breathing Disorders, and parent report of child currently participating in psychological therapy.. These data will be stored via the secure REDCap database, accessible only by the study team.

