22-item using 3 point scale (yes = 1, no= 0, don’t know = missing). Number “yes” items divided by total number of items responded, with scores ranging from 0-1. Scores >0.33 considered positive and suggestive of high risk for a pediatric sleep-related breathing disorder.

Does your child currently receive psychological therapy?

Enrolled subject data to be collected

Concept	Measure
Demographics	Parent-report survey includes information about parental characteristics (age, gender, education, race, ethnicity, household income) and child characteristics (age, gender, grade level, race, ethnicity, JIA type, and medications). Child Health Assessment Questionnaire -parent report measure that assesses daily activities and functional impairment due to chronic pain in child.
Self-Management Measures (treatment group only)	Self-Efficacy - 9-item parent & 5-item children report of their confidence in carrying out sleep-related behaviors using 10-point Likert scale (1=not confident at all, 10=totally confident). Higher scores indicate higher self-efficacy. Index of self-regulation - 12-item parents & child report of motivation (recondition, stimulus control, behavioral monitoring) Patient activation measure - 13-item parent & child report of knowledge, skill, & confidence for self-management. Goal Setting: engagement in goal setting will be tracked on the SLEEPSMART web-based application using # and type of goals created; # of goals tracked; and rate of goal completion. Sleep Problem questionnaire- 4 item child report of their readiness to change their sleep habits. Credibility /expectations Questionnaire: 6-item parent report questionnaire to rate treatment expectancy

Sleep	
	Child Sleep Habits Questionnaire (CSHQ) 45-item retrospective report of child sleep habits over typical week using 3 point Likert scale. Higher scores indicate greater likelihood of sleep disturbance, with >41 as the cut-point for clinically significant sleep disturbance. Eight sleep subscales include bedtime resistance, sleep onset delay, sleep duration, sleep anxiety, night awakenings, parasomnias, sleep-disordered breathing, and daytime sleepiness.
	Children's /Adolescent Sleep Wake Scale – 25-item child report measure of sleep quality over the last month; includes 5 domains: going to bed, falling asleep, maintaining sleep, reinitiating sleep, and returning to wakefulness. A total score indicates overall perception of sleep quality

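### Exclusion criterion 6 for children is worded so that it bars every child not in psychological therapy; the direction is probably inverted and is corrected nowhere in the documents

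*Combined protocol and SAP*

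**What the plan says.** Section 2.2 opens the list with "Exclusion criteria for JIA children include" and closes it, as item 6, with "child is not currently participating in psychological therapy". The item just before it is "children who do not speak English".

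Therapy status is then used in screening for Aim 3:

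- Section 4.1 has parents complete online screening that asks "is your child currently receiving psychological therapy". It adds: "Instruments are automatically scored within REDCap and indicates whether participants appear to meet eligibility criteria or not". Families who are not eligible are thanked; those who are eligible are told that the team will contact them.
- Section 4.7 keeps, as screening data, "parent report of child currently participating in psychological therapy".
- Section 5.2 lists the screening item as "Does your child currently receive psychological therapy".

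The exclusion list under Participants in the Research Strategy does not mention psychological therapy. It excludes co-morbid conditions, with ADHD and depression as examples, which Section 2.2 does not list.

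**The concern.** A negated statement in an exclusion list reverses who may enter. Taken at its word, criterion 6 keeps only children already receiving a psychological co-intervention that could itself affect sleep and self-management.

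This is the written entry rule for the randomised trial, and anyone who programs, applies or audits eligibility would work from it. There are two ways to go wrong. If the rule is followed, the trial enrols a different population from the one it appears to be about. If staff apply the presumed intent instead, every enrolled child who is not in therapy meets a written exclusion criterion, and the approved protocol disagrees with the enrolled sample.

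**Working it through.** No formula in the plan bears on this point and there is no stated figure to reproduce. The check is a reading of the criterion within its list, followed by a comparison with every other mention of therapy status.

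**Step 1: how the list is built.** The other five child exclusions are a diagnosed sleep disorder, a positive Pediatric Sleep Questionnaire screen (above 0.33), no daily internet or mobile device, developmental delay, and not speaking English. Each names the state that disqualifies. Two of them are negative in form (no access, no English), and there the negative state is the one that disqualifies. A negation in this list is therefore not self-correcting, and criterion 6 has to be read in the same way.

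**Step 2: the literal result.**

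- In therapy: not excluded by criterion 6.
- Not in therapy: excluded by criterion 6.

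If the negation is a slip, or the phrase belongs in the inclusion list, the two lines swap completely.

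**Step 3: does another section settle the direction?**

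- Sections 4.1 and 5.2: a positive question, with no disqualifying answer.
- Sections 4.2 and 4.7: therapy status is collected, with no direction.
- Research Strategy: no therapy criterion.

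The other Aim 3 screening items do carry a rule in Section 5.2. A yes to either sleep question qualifies, and a score above 0.33 on the breathing scale counts as positive. Therapy is the one screening item without a rule beside it, so criterion 6 is its only written direction.

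**Step 4: what supports the inference of a slip.** No aim, background or recruitment section describes a study of children already in therapy. The Usual Care paragraph of the Research Strategy does not list psychological therapy as part of usual care. The Research Strategy excludes depression as a co-morbidity, which fits poorly with requiring therapy. The same sentence in Section 2.2 has other drafting slips in its numbering. This makes an inversion probable, but no section states the intended direction or a reason for the criterion.

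**Step 5: size.** Let p be the share of otherwise eligible children who are in therapy. The literal rule keeps p; the reverse rule keeps 1 − p. The literal pool is the smaller of the two whenever p is below one half. The documents do not give p. As an assumption only, p = 5% gives 5% against 95% (a ratio of 1 to 19), and p = 20% gives 20% against 80% (1 to 4). The finding does not depend on these values.

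**The case against.** The strongest reply is that nobody would apply the rule literally. The intent looks plain, the screening question is worded positively, and people stand between the REDCap result and enrolment: the clinical research associate screens telephone callers from a script, and the team contacts families who pass online. Those scripts and the survey files are not among the documents, and they may state the direction. On this view the point is a wording slip with hypothetical consequences.

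Much of this stands, and it limits what can be claimed. Three stronger readings are tempting and are not supported:

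- *The wrong children have been or will be enrolled.* A reader might infer this from the automatic scoring. The documents do not show how REDCap is coded, so mis-enrolment is not established.
- *The usual-care comparison would be confounded with therapy.* Under the literal rule every child in both arms would be in therapy, and Section 5.1 assigns arms by blocked randomisation after baseline. A factor shared by all participants cannot confound the contrast. It could change the size of the effect and the children to whom it applies.
- *The loss can be counted from the 250 clinic patients in Section 2.1.* That figure covers ages 9 to 11 at the Seattle clinic, is given under Aims 1 and 2, and is not filtered for sleep difficulty or the other criteria. Aim 3 recruits ages 8 to 13 from two clinics and social media.

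What does not stand is that a guessable intent removes the need for correction. The two readings select opposite populations, and the only written direction is the improbable one.

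**Conclusion.** The point holds as a defect in an operative entry rule. As written, criterion 6 excludes children who are not in psychological therapy, and nothing in the supplied documents corrects it. The wording error is certain on the page. That the opposite was meant is a strong inference, which the sponsor must confirm.

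The consequence, if the rule were applied as written, is a changed target population, a smaller recruitment pool (provided that fewer than half of otherwise eligible children are in therapy), and pilot effect sizes that may not carry over to the definitive trial they are meant to inform. The validity of the randomised comparison is not affected, and neither is any alpha, power or sample size figure. The scale of the recruitment loss cannot be determined from the documents.

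**What to change.** - The sponsor should confirm which therapy status is meant to disqualify a child.
- Depending on the answer, correct criterion 6 in Section 2.2 or move its present wording to the inclusion list.
- State the disqualifying answer beside the screening question in Sections 4.1 and 5.2.
- Reconcile Sections 2.2, 4.1, 4.7 and 5.2 with the Research Strategy exclusion list, which has no such criterion.
- Verify that the REDCap eligibility logic follows the confirmed direction, and check any children already screened against it.

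The cost is one line of protocol text, matching edits where the item recurs, and a check of the scoring logic. The design and the analysis do not change.

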3 RESEARCH SETTING

3.1 Reason for sites. Describe the reason(s) why you selected the sites where you will conduct the research.

We selected Seattle Children's and CHOP Pediatric Rheumatology clinics as our recruitment sites because the clinicians manage and care for children with JIA. We will also recruit JIA children outside of WA state via social media.

3.2 Local context. Culturally-appropriate procedures and an understanding of local context are an important part of protecting subjects. Describe any site-specific cultural issues, customs, beliefs, or values that may affect your research or how it is conducted.

Examples: It would be culturally inappropriate in some international settings for a woman to be directly contacted by a male researcher; instead, the researcher may need to ask a male family member for permission before the woman can be approached. It may be appropriate to obtain permission from community leaders prior to obtaining consent from individual members of a group.

This federal site maintains an international list of human research standards and requirements:

<http://www.hhs.gov/ohrp/international/index.html>

In our prior research studies in which we recruited from Seattle Children's, we did not encounter cultural challenges with our measures or use culturally inappropriate procedures. We do not anticipate site-specific cultural issues, customs, or beliefs that would affect our research and how it is conducted.

3.3 Site-specific laws. Describe any local laws that may affect your research (especially the research design and consent procedures). The most common examples are laws about:

- **Specimens** – for example, some countries will not allow biospecimens to be taken out of the country.
- **Age of consent** – laws about when an individual is considered old enough to be able to provide consent vary across states, and across countries.
- **Legally authorized representative** – laws about who can serve as a legally authorized representative (and who has priority when more than one person is available) vary across states and countries.
- **Use of healthcare records** – many states (including Washington State) have laws that are similar to the federal HIPAA law but that have additional requirements.

3.4 Site-specific administrative or ethical requirements. Describe local administrative or ethical requirements that affect your research.

Example: A school district may require you to obtain permission from the head district office as well as school principals before approaching teachers or students; a factory in China may allow you to interview factory workers but not allow you to pay them.

None

4 RECRUITING and SCREENING PARTICIPANTS

4.1 Recruiting and Screening. Describe how you will identify, recruit, and screen subjects. Include information about: how, when, where, and in what setting. Identify who (by position or role, not name) will approach and recruit subjects, and who will screen them for eligibility.

Recruitment

Recruitment will use several methods: SCH Rheumatology clinic; letters to JIA parents seen at SCH; posted recruitment flyers, social media posts.

The below is broken down by Aims:

Aims 1 & 2: will involve recruitment of 15 *JIA children and their parent* to do semi-structured interviews and test out the online modules.

Recruitment

Letters to JIA parents whose children are cared for at SCH, will be sent describing the study, and will include the clinical research associate's (CRA) contact information for questions.

SCH: JIA participants and their parents. The CRA will review the Rheumatology patient list for eligible child. A list of names and addresses for children who meet the above criteria will be obtained from the database and maintained by the CRA in a secure area. Potential subjects with JIA will be mailed a letter informing them about the study, and provide the CRAs contact information. During the clinic visit, the CRA will give eligible child and their parents the study flyer that includes information about the study at a clinic visit. (See Aims 1_2 Recruitment).

Aim 3: will involve 60 JIA children (8 to 13 years) and their parent, and the focus is on feasibility and acceptability of the online sleep (SLEEPSMART) intervention. 30 children will be randomized using an online program to the active treatment group (online sleep intervention- SLEEPSMART), and 30 will be in the control group.

The CRA will review the Rheumatology patient list for eligible child. A list of names and addresses for children who meet the above criteria will be obtained from the database and maintained by the CRA in a secure area. The CRA will contact potential subjects with JIA via the telephone to inform them about the study. Participants who are interested and/or unsure about the study, the CRA will email eligible child and their parents the study flyer that includes information about the study, and guide potential participants to <https://www.sleepsmartstudy.org/> webpage, and will include the CRA contact information with questions..

Recruitment flyers will be posted in community-based pediatric primary care clinics, rheumatology clinics, recreational centers, and boys and girls clubs within and outside WA state.

Social Media posts will describe the study, and provide a link to the online screening webpage as well as the Clinical Research Associate (CRA) contact information. Posts may be made to UW School of Nursing

webpage/social media accounts, and Facebook. Posts will guide potential participants to <https://www.sleepsmartstudy.org/> webpage.

SCH: JIA participants and their parents. The CRA will review the Rheumatology patient list for eligible child. A list of names and addresses for children who meet the above criteria will be obtained from the database and maintained by the research coordinator in a secure area. Potential subjects with JIA will be called informing them about the study that will guide potential participants to <https://www.sleepsmartstudy.org/> webpage, and provide the CRAs contact information.

CHOP: Rheumatology staff at CHOP will review the Rheumatology database for eligible children. Staff at CHOP will mail eligible participants a letter informing them about the study that will guide potential participants to <https://www.sleepsmartstudy.org/webpage>. Interested participants will contact the CRA, who works at SCH, with questions.

Screening: The CRA at SCH will review the Rheumatology patient list for eligible youth. A list of names and addresses for children who meet the above criteria will be obtained from the database and maintained by the CRA in a secure area. Potential subjects with JIA will be called by the CRA who will inform them about the study. Interested participants will contact the CRA with questions.

Aims 1 & 2: Interested potential participants will contact the CRA by phone. For those who contact the CRA by phone, the CRA will screen potential participants initially over the phone (see Aims 1_2 Recruitment Script).

Aims 3: Interested potential participants may choose to visit <https://www.sleepsmartstudy.org/webpage> or contact the CRA by phone. For those who contact the CRA by phone, the CRA will screen potential participants initially over the phone (see Recruitment Script). For those who are eligible and interested, they will be directed to the <https://www.sleepsmartstudy.org/webpage> webpage (hosted by REDCap). From there, parents may complete the screening surveys including “does your child has difficulty with sleep quality and/or does poor sleep impact your child’s day-to-day function (school, interacting with peers, hobbies)?” Sleep-Related Breathing Disorder Scale from the Pediatric Sleep Questionnaire (SRBD) and is your child currently receiving psychological therapy. Instruments are automatically scored within REDCap and indicates whether participants appear to meet eligibility criteria or not. Those who are not eligible are thanked for their time. Those that are eligible are advised that the study team will contact them (see recruitment follow-up script).

REDCap uses unique identifiers for potential participants and only the CRA and PI has the master list connecting potential participant email, names, and identifiers.

4.2 Recruitment materials.

a. What materials (if any) will you use to recruit and screen subjects?

Examples: talking points for phone or in-person conversations; video or audio presentations; websites; social media messages; written materials such as letters, flyers for posting, brochures, or printed advertisements; questionnaires filled out by potential subjects.

Aim 1 & 2: Study flyer, letters to participants, Child Sleep Habits Questionnaire (CSHQ), Sleep-Related Breathing Disorder Scale from the Pediatric Sleep Questionnaire (SRBD) will be used to recruit and screen subjects.

Aim 3: Study flyer, letters to participants, social media posts, <https://www.sleepsmartstudy.org/webpage> , phone scripts, “does your child has difficulty with sleep quality and/or does poor sleep impact your child’s day to day function?” Sleep-Related Breathing Disorder Scale from the Pediatric Sleep Questionnaire (SRBD), and parent report if the child is currently receiving psychological therapy will be used to recruit and screen subjects.

b. Upload descriptions of each type of material (or the materials themselves) to the **Consent Forms and Recruitment Materials SmartForm of **Zipline**.** If you will send letters to the subjects, the letter should include a statement about how you obtained the subject's name, contact information, and any other subject-specific information (such as a health condition) that is mentioned in the letter.

HSD encourages researchers to consider uploading descriptions of most recruitment and screening materials instead of the materials themselves. The goal is to provide the researchers with the flexibility to change some information on the materials without submitting a Modification for IRB approval of the changes. Examples:

- You could provide a list of talking points that will be used for phone or in-person conversations instead of a script.
- For the description of a flyer, you might include the information that it will provide the study phone number and the name of a study contact person (without providing the actual phone number or name). In doing so, you would not need to submit a Modification if/when the study phone number or contact person changes. Also, instead of listing the inclusion/exclusion criteria, you might state that the flyer will list one or a few of the major inclusion/exclusion criteria.
- For the description of a video or a website, you might include a description of the possible visual elements and a list of the content (e.g., study phone number; study contact person; top three inclusion/exclusion criteria; payment of \$50; study name; UW researcher).

4.3 Relationship with participant population. Do any members of the study team have an existing relationship with the study population(s)?

Examples: a study team member may have a dual role with the study population (for example, being their clinical care provider, teacher, laboratory directory or tribal leader in addition to recruiting them for his/her research).

	No
	Yes

→ If yes, describe the nature of the relationship.

Pediatric Rheumatologists are the clinical care providers for child with JIA

4.4 Payment to participants. Describe any payment you will provide, including:

- The total amount/value
- Whether payment will be "pro-rated" so that participants who are unable to complete the research may still receive some part of the payment

The IRB expects the consent process or study information provided to the subjects to include information about the number and amount of payments, and especially the time when subjects can expect to receive payment. One of the most frequent complaints received by HSD is from subjects who expected to receive cash or a check on the day that they completed a study and who were angry or disappointed when payment took 6-8 weeks to reach them.

Do not include a description of any expenses that will be reimbursed.

Aim 1 & 2: Participants will receive a \$25 gift card for each interview (2-3 interviews are anticipated), and \$40 gift care to test the online module. Total estimated to be \$90 - \$115 depending if 2 or 3 interviews are needed.

Aim 3: Participants who agree to participate in this study will receive a monetary incentive of up to \$310 per dyad (in VISA gift cards). The compensation will be divided into four portions such that:

\$75 gift card will be given at the completion of T1 (baseline assessment), after completion of the 10 days of actigraphy and sleep diary). Gift card will be mailed to participant home.

\$110 gift card will be given after T2 (immediately post SLEEPSMART intervention). Gift card will be mailed to participant home.

\$125 gift card will be given after T3 (1 month after intervention) and 10 days of actigraphy and sleep diary). Gift card will be mailed to participant home.

4.5 Non-monetary compensation. Describe any non-monetary compensation you will provide. Example: extra credit for students; a toy for a child. If you will be offering class credit to students, you must provide (and describe) an alternate way for the students to earn the extra credit without participating in your research.

N/A

4.6 Consent for recruiting and screening. Will you obtain consent for any of the recruiting and screening procedures? ([Section 8: Consent of Adults](#) asks about consent for the main study procedures).

"Consent" includes: consent from individuals for their own participation; parental permission; assent from children; consent from a legally authorized representative for adult individuals who are unable to provide consent.

Examples:

- For a study in which names and contact information will be obtained from a registry: the registry should have consent from the registry participants to release their names and contact information to researchers.
- For a study in which possible subjects are identified by screening records: there will be no consent process.
- For a study in which individuals respond to an announcement and call into a study phone line: the study team person talking to the individual may obtain non-written consent to ask eligibility questions over the phone.

No → If no, you must still answer [question 4.7](#) below.

Yes → If yes, describe the consent process.

We will not obtain consent for pre-screening medical records for eligibility and PHI (diagnosis, name, contact information etc.)

Aim 1 & 2: Potential study subjects will respond to a letter by calling (or in person during the clinic visit) with the CRA. The CRA will complete a screening process to determine if subjects meet eligibility requirements

Aim 3: Potential study subjects will respond to the CRA by a telephone call or email. . The CRA will complete a screening process to determine if subjects meet eligibility requirements and/or participants will opt-in for screening procedures via <https://www.sleepsmartstudy.org/webpage> . If they have questions, they are advised to contact the CRA, who will follow-up by phone using the Recruitment Script and answer any questions.

a. Documentation of consent. Will you obtain a written or verifiable electronic signature from the subject on a consent form to document consent for all of the recruiting and screening procedures?

No → If no, describe the information you will provide during the consent process and for which procedures.

Aim 3: Participants will opt-in for screening procedures via <https://www.sleepsmartstudy.org/webpage> . If they have questions, they are advised to contact the CRA, who will follow-up by phone using the Recruitment Script and answer any questions.

Yes → If yes, upload the consent form to the **Consent Forms and Recruitment Materials** page of **Zipline**.

4.7 Data and specimens for recruiting and screening. For studies where you will obtain consent, describe any data and/or specimens (including any PHI) you will obtain for recruiting and screening (prior to obtaining consent) and whether you will retain it as part of the study data.

Obtain means to possess or record in any fashion (writing, electronic document, video, email, voice recording, etc.) for research purposes and to retain for any length of time.

Examples: names and contact information; the information gathered from records that were screened; results of screening questionnaires or screening blood tests; Protected Health Information (PHI) from screening medical records to identify possible subjects.

Screening information includes:

Parent first name, email address, phone number, and preferred mode of contact (text, phone, email) for follow-up.

Also includes child first name, age, gender, and duration of JIA will be obtained to ensure study eligibility, and be retained as part of the study data. Additional information includes screening surveys: “does your child has difficulty with sleep quality and/or does poor sleep impact your child’s day to day function?” and Sleep-Related Breathing Disorders, and parent report of child currently participating in psychological therapy.. These data will be stored via the secure REDCap database, accessible only by the study team.

